2.4.2 Secondary endpoints/outcomes

- Proportion of patients with HIV-RNA viral load < 50 copies/mL at week 24, 36, 48
- HIV-1 drug resistance at confirmed virological failure (genotype)
- Time to reach CD4 count > 200/ μ L (first measurement)
- Proportion of patients with CD4 cell count < 200 μ L and < 350 μ L at week 4, 8, 12, 24, 36, 48
- CD4/CD8 ratio at week 4, 8, 12, 24, 36, 48
- Incidence of IRIS in the two arms through week 48
- Incidence and duration of hospitalisation, rate of relapse of specific OI/BI through week 48
- Safety and tolerability, measured by Grade 2, 3 and 4 signs and symptoms and laboratory toxicities through week 48
- ART and OI/BI treatment changes and dose modifications due to toxicities and DDI with ART, and IRIS through week 48
- Health care resource use, including total inpatient days and emergency room visits through week 48
- QOL and functional status outcomes, including overall self-reported QOL and functional status compared in the two groups at week 48
- Discontinuation or modification of study medication due to insufficient virological response, resistance mutations at baseline, or resistance mutation development before week 48

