6.1.5 The randomisation scheme

Patients will be randomly allocated (1:1) to receive a BIC containing regimen or boosted PI containing regimen for 48 weeks. Randomisation will be computer-generated in permuted blocks and stratified by country and baseline CD4 cell count (<50 cells/ μ L, 50-199 cells/ μ L, or \geq 200 cells/ μ L). Randomisation will be done at the baseline visit (date of the study treatment initiation). This study is open-label, therefore, all investigators, site pharmacists, study nurses and subjects will be unmasked and aware of the treatment allocation throughout the study.

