9.3.3 Secondary outcome analysis

All secondary outcome analysis will be done with the ITT population. The p-values will be two-tailed, with a significant level of 0.05.

The proportion of patients with HIV-ribonucleic acid (RNA) viral load <50 copies/mL at week 48 will be analysed using the snapshot approach. Fisher's exact test will be used to compare the estimated proportion between the two groups.

A genotypic resistance test will be performed in all patients with virological failure. Drugs resistance mutations will be identified from the International AIDS Society (IAS)-USA resistance testing panel (last version at the time of analysis) and for BIC we will use IAS, Agence Nationale de Recherches sur le SIDA (National Agency for AIDS Research) (ANRS) or Royal College of Physicians (RCP) lists to perform the analysis whenever they will be made available. Resistance to BIC will also be identified using phenotypic resistance test. Fisher's exact test will be used to compare the presence of at least one drug resistance mutation between the 2 groups.

The median time to reach CD4 cell count >200/ μ l will be estimated using the Kaplan-Meier method, censoring at week 48 or last follow-up date if not seen at week 48. Time to reach CD4 cell count >200/ μ l will be defined as the time between the date of study treatment initiation (baseline, week 0) and the date of which patient reached CD4>200/ μ l. The log-rank test will be used to compare the two survival functions. The p-values will be two-tailed, with a significant level of 0.05. The proportion of patients with CD4 cell count <350/ μ l at week 48 will be done with the ITT population, with the last observation carried forward (LOCF) approach. Fisher's exact test will be used to compare the 2 groups.

The median change in CD4/CD8 ratio from baseline to week 48 will be analysed with the ITT population, with the LOCF approach. The non-parametric Mann Whitney test will be used to compare the change from baseline between the 2 groups.

The incidence of IRIS will be analysed with the Kaplan-Meier method. The Log-rank test will be used to compare the two survival functions. The effect of study treatment on IRIS will be assessed using Cox regression model with treatment group and adjustments for stratification factors.

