The incidence of hospitalisation will be estimated by the Kaplan-Meier estimate. The Log-rank test will be used to compare the two survival functions. The duration of hospitalisation will be estimated by the cumulative days of hospitalisation during the course of study and will be compared between the 2 groups by using the Mann-Whitney test. The rate of relapse/recurrence will be estimated by the number of patients with relapse/recurrence divided by the total number patients in ITT population. Fisher's exact test will be used to compare the 2 groups.

The frequency of each Grade 2, 3 or 4 AEs, laboratory toxicities, and ART and OI/BI treatment changes and dose modifications due to toxicities and IRIS will be described and compared by group. Fisher's exact test will be used to compare the 2 groups.

The proportion of patients with health care resource use, and emergency room visits will be compared in the two groups with Fisher's exact test. The total inpatient days will be estimated by the cumulative inpatient days during the course of study and will be compared between the 2 groups by using the Mann-Whitney test.

To assess the impact of study treatment on the evolution of QOL at week 48, we will use multiple imputation approach to replace missing values. We will compare the treatment effect on QOL on each of the 5 datasets generated, including the imputed values, and the results will be combined with Rubin's rules. A generalized estimating equation (GEE) model will be used.

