6.3.2 Baseline data

The following demographic characteristics will be summarized by treatment group and overall:

- Age
- Sex
- Child bearing potential among Female
- Participating country
- Ethnicity (e.g White caucasian; White mixed; Asian, Black; Other)
- Population group (AIDS with any CD4 cell count; Severe bacterial infection and CD4 cell count < 200; Asymptomatic with CD4 cell count < 100; Currently receiving treatment for an opportunistic infection)
- Body weight and BMI
- Systolic and diastolic Blood Pressure
- Pulse rate
- Alcohol intake (Does not drink alcohol; Drink alcohol)
- Smokers (Never smoked; Current smoker; Ex-smoker)
- Recreational drug use
- Days from HIV diagnosis to treatment initiation
- HIV RNA viral load, log10 copies/mL and in category (<100,000; 100,000-500,000; >500,000)
- CD4+ count (cells/ μ L) and in category (<50; 50-199; \geq 200) and CD4+ (%)
- CD8+ count (cells/ μ L) and CD8+ (%)
- CD4/CD8 ratio and in category (<0.10; 0.10-0.30; >0.30)
- Positive HBV Antigen; Positive HCV antibody:
- HCV RNA Viral load among those with Positive HCV antibody
- Positive TB testing result
- Red blood cells ($10^{12}/L$);
- White blood cells ($10^{12}/L$)
- Platelet counts ($10^9/L$)
- Haemoglobin (g/dL)
- Haematocrit (%)
- MVC (fl)
- MCH (pg)
- Neutrophils ($10^{12}/L$)
- Lymphocytes ($10^{12}/L$)
- Monocytes ($10^{12}/L$)
- Eosinophils ($10^{12}/L$)
- Basophils ($10^{12}/L$)
- Sodium (mmol/L)
- Potassium (mmol/L)
- Total Protein (mmol/L)
- Total Bilirubin (μ mol/L)
- Indirect bilirubin (μ mol/L)
- ALT (U/L); AST (U/L)
- Albumin (g/L)
- Creatinine (umol/L); Creatinine clearance (eGFR) (mL/min)
- Alkaline phosphatase (U/L)
- Creatine phosphokinase (U/L)
- Calcium (mmol/L)
- Phosphate (mmol/L)
- Urea (mmol/L)

- Chloride (mmol/L)
- Total cholesterol (mmol/L); HDL-cholesterol (mmol/L); LDL-cholesterol (mmol/L); Triglyceride (mmol/L);
- Glucose (mmol/L)
- Resistance mutations at baseline. Drugs resistance mutations will be identified from the Stanford drugs resistance interpretation algorithm (last version at the time of analysis).
<https://hivdb.stanford.edu/dr-summary/mut-scores/NRTI/>;
<https://hivdb.stanford.edu/dr-summary/mut-scores/NNRTI/>; <https://hivdb.stanford.edu/dr-summary/mut-scores/PI/>; <https://hivdb.stanford.edu/dr-summary/mut-scores/INSTI/>.

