7.2.7 Incidence of IRIS

Endpoints

The endpoint is the first occurrence of IRIS over the 48-week visit. IRIS diagnosed at baseline will not be considered in the analysis.

Descriptive statistics and graphical representation

The analyses will be performed with the mITT population and DPS1. Data will be summarized with the number and percentage of participants with an IRIS. Kaplan-Meier curves will also be plotted.

Statistical methodology

The incidence of IRIS will be estimated with the Kaplan-Meier method. The follow-up will begin at baseline (date of study treatment initiation) and continue until the week 48 visit, study discontinuation or death, loss to follow-up, or onset of IRIS; whichever occurs first.

The effect of study treatment will be assessed using Cox regression model with treatment group and adjustments for stratification factor (country/group of neighbouring countries and baseline CD4 cell counts (<50 or $\geq 50/\mu\text{L}$)). An adjusted hazard ratio (HR) and the associated 95% Confidence Interval (CI) will be calculated.

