Given the paucity of data for a clearly-defined immune reconstitution inflammatory syndrome for each opportunistic pathogen, the IRIS Working Group concentrated on developing specific definitions for the most well-characterized IRIS in the literature. IRIS events may occur as paradoxical worsening or as an unmasking. Paradoxical responses are described as an initial clinical worsening when patients are started on pathogen-specific therapy and/or ART simultaneously. Unmasking refers to aberrant clinical presentations of previously common OIs such as localized *Mycobacterium avium complex* (MAC) lymphadenitis and *Cytomegalovirus* (CMV) vitritis occurring within the first weeks of starting ART suggesting that patients have sub-clinical disease prior to the initiation of ART. There are specific definitions including confirmed and probable for the following specific pathogen IRIS: *Mycobacterium avium complex* (MAC), Progressive Multifocal Leukoencephalopathy (PML), *Cytomegalovirus* (CMV), *Mycobacterium tuberculosis* (TB) and *Cryptococcus neoformans*. All other clinical syndromes attributed to immune reconstitution will be treated as probable IRIS events without specific definitions and will include *Pneumocystis jirovecii pneumonia* (PCP), *Varicella Zoster* (VZV), *Herpes Simplex* (HSV), *Hepatitis B*, *Hepatitis C*, *Toxoplasmosis*, *Kaposi's Sarcoma*, *Graves' disease*, *Sarcoidosis*, and other autoimmune disorders. For these less well-defined IRIS, key data will be captured on a generic form that includes clinical signs/symptoms, CD4, HIV RNA data, and clinical outcomes.

Specific IRIS Case Definitions

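### The SAP models for first IRIS and first hospitalisation leave out the patient's entry condition, a collected and plausibly prognostic baseline item; adding it is a free gain in precision

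*Combined protocol and SAP*

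**What the plan says.** Protocol 2.4.2 and SAP 2.2.2 list "Incidence of IRIS in the two arms through week 48" as a secondary endpoint, and hospitalisation over the same period as another. For both, SAP 7.2.7 and 7.2.8 use the same sentence: "The effect of study treatment will be assessed using Cox regression model with treatment group and adjustments for stratification factor". The factors named are country (or group of neighbouring countries) and baseline CD4 in two levels, <50 and ≥50/µL. Protocol v5.0, 9.3.3, says for IRIS: "The effect of study treatment on IRIS will be assessed using Cox regression model with treatment group and adjustments for stratification factors", alongside a log-rank test. For hospitalisation it gives only the log-rank test: "The incidence of hospitalisation will be estimated by the Kaplan-Meier estimate. The Log-rank test will be used to compare the two survival functions".

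Randomisation is "stratified by country and baseline CD4 cell count" (protocol 6.1.5), so entry condition is not a stratum. Inclusion criterion 4 (protocol v5.0, 5.1) requires each patient to qualify by at least one of four routes: (a) AIDS at any CD4; (b) severe bacterial infection with CD4 <200; (c) CD4 <100; (d) treatment for an opportunistic infection. SAP 6.3.2 lists this as a baseline item, beginning "Population group (AIDS with any CD4 cell count; Severe bacterial infection and CD4 cell count < 200". The SAP section 9 subgroup list concerns the primary endpoint only and does not include it. Nothing in the protocol or SAP brings entry condition into the IRIS or hospitalisation comparison as a covariate, stratum or sensitivity analysis.

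**The concern.** Criterion 4 admits two kinds of patient: those who arrive with an AIDS-defining condition or serious infection, and those who arrive with a low CD4 count alone. The documents give qualitative reasons to expect different risks. On IRIS, SAP Appendix 4 states: "Paradoxical responses are described as an initial clinical worsening when patients are started on pathogen-specific therapy and/or ART simultaneously". Its case definitions for CMV, cryptococcal, MAC, TB and PML IRIS are all split by whether that infection was already known. On hospitalisation, a severe bacterial infection at entry can itself be defined by an unscheduled admission (footnote to criterion 4b).

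IRIS incidence is a named secondary objective, and the protocol background describes conflicting evidence on IRIS with integrase inhibitors. Leaving out a prognostic variable that is already collected gives up precision, leaves any chance imbalance in entry condition uncorrected, and pulls the estimated hazard ratio somewhat towards 1.

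**Working it through.** **Step 1. The plan's own figure (SAP section 4).** Inputs: failure 25% v 23%, margin 37% v 25%, two-sided 5%, 80% power.

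- Margin HR = ln(0.63)/ln(0.75) = 1.606. Expected HR = ln(0.77)/ln(0.75) = 0.909.
- Events = 4(1.960 + 0.842)² / [ln(1.606/0.909)]² = 31.40/0.3239 = 96.9, so 97.
- N = 97/0.24 = 404. Allowing for 7.5% dropout, 404/0.925 = 437, against 440 planned.

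The design reproduces and is not in dispute. No rate, size or power is given for IRIS or hospitalisation alone, so every rate below is an assumption.

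**Step 2. Does the CD4 term already carry the information?** Not fully. Route (c) needs CD4 <100 and route (b) CD4 <200. Apart from change between screening and baseline, patients at CD4 ≥100 must therefore have entered by (a), (b) or (d), and those at ≥200 by (a) or (d). The SAP level ≥50 pools all of these with patients at 50–99, who may have low CD4 only.

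**Step 3. Chance imbalance, 220 per arm.** Let p be the share entering with a qualifying condition. The SE of the between-arm difference is √[2p(1−p)/220].

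- p = 0.5: SE = 0.0477, 95% limit 9.3 points. p = 0.3 or 0.7: SE = 0.0437, 95% limit 8.6 points.
- If the condition carries hazard ratio h and treatment has no effect, the apparent treatment HR is roughly (a·h + 1 − a)/(b·h + 1 − b), where a and b are the two arms' shares. At p = 0.5 and h = 3: a = 0.5467, b = 0.4533, giving 2.0934/1.9066 = 1.098.
- Over p = 0.3 to 0.7, an imbalance at the 95% limit gives 1.03–1.04 for h = 1.5, 1.07–1.11 for h = 3 and 1.09–1.17 for h = 5.

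**Step 4. Power with and without the covariate.** Simulated trials: 220 per arm, exponential event times over 48 weeks, 7.5% per year dropout, 50% entering with the condition, CD4 <50 in half of patients with hazard ratio 1.5 and in both models, two-sided 5% Wald test, 2,000 runs per case. Incidence is the control-arm figure. Power is shown as planned → with covariate, in %:

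| Endpoint, incidence, treatment HR | h = 1.5 | h = 3 | h = 5 |
|---|---|---|---|
| IRIS 5%, 2.5 | 74.8 → 74.7 | 73.3 → 74.7 | 72.4 → 73.3 |
| IRIS 10%, 2.0 | 74.1 → 74.2 | 73.8 → 75.6 | 70.8 → 73.6 |
| Hospitalisation 25%, 1.6 | 74.9 → 75.6 | 71.0 → 75.0 | 66.1 → 74.8 |
| Hospitalisation 40%, 1.5 | 81.1 → 81.9 | 74.5 → 81.2 | 67.2 → 79.9 |

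The simulation error of each power figure is about √(0.75 × 0.25/2000) = 1 point, so the IRIS gains are barely above noise. A separate IRIS case (40% entering with the condition, 15% v 3% incidence, hence 0.4 × 15 + 0.6 × 3 = 7.8% overall, treatment HR 2.0) gave 62 → 66. That is slightly larger, with a prognostic hazard ratio of ln(0.85)/ln(0.97) ≈ 5.3.

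Varying the share for hospitalisation at 25% and h = 5 gave 64.7 → 75.0 at 30% and 72.3 → 77.0 at 70%. With no treatment effect, rejection was 4.4–5.1% across both models. In the strongest case (40% hospitalised, h = 5) the planned model estimated a true conditional HR of 1.50 as about 1.41.

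Limits: the simulation omits country and treats CD4 and entry condition as independent, which Step 2 shows they are not.

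**The case against.** The strongest reply is that nothing here is an error. Randomisation plus adjustment for the stratification factors is a standard, valid analysis, and an extra covariate on secondary endpoints is optional. That stands, and it limits the point to efficiency.

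A reader might go further and infer that entry infection is the main predictor of IRIS. The documents do not support that. The same IRIS appendix describes unmasking disease, which can arise in patients with no recognised infection at entry, and says it is the more common form for PML. Exclusion 7 keeps out active TB and cryptococcal meningitis. The appendix reports few clear cases of PCP IRIS and very little data on toxoplasmosis IRIS. Nothing ranks entry condition above CD4, which is already in the model.

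A reader might also expect larger IRIS gains by assuming control-arm incidence of 15% or 24%. The only related figure in the documents is 12.2% per year for a composite that already includes IRIS along with other severe morbidity and death (SAP section 4). Milder IRIS could fall outside that composite, but rates above it have no support here.

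Nor are the comparisons unadjusted: both SAP models carry country and CD4. Only the protocol's log-rank tests have no covariates.

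One objection changes the remedy. The entry routes are joined by *or* and overlap: a patient with an opportunistic infection and CD4 <100 may meet (a), (c) and (d). Criterion 4c in protocol v5.0 covers patients with or without symptoms, while SAP 6.3.2 still labels that group asymptomatic. Route (a) also admits non-infectious conditions such as lymphoma or wasting (protocol Appendix 3). A single ticked criterion would therefore misclassify patients.

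**Conclusion.** The omission is confirmed in SAP 7.2.7 and 7.2.8. It causes neither bias nor inflated type I error. It forgoes some precision and leaves chance imbalance in entry condition uncorrected. Under the stated assumptions the loss is negligible to small for IRIS. For hospitalisation it can be material, but only if entry condition is strongly prognostic and admission is common. Both conditions are assumptions, since the documents support the link in kind but give no strength for it. This is a free improvement to a secondary analysis and has no bearing on the sample size or the primary comparison.

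**What to change.** In SAP 7.2.7 and 7.2.8, add one prespecified binary covariate to the Cox model: AIDS-defining condition, severe bacterial infection, or opportunistic infection (under treatment or recently treated) at entry, yes v no (low CD4 only). Derive it from baseline medical history together with the entry criteria, and state that meeting any of 4a, 4b or 4d takes precedence over 4c. Align the asymptomatic label in SAP 6.3.2 with criterion 4c. Report the resulting adjusted hazard ratio in SAP Table 4.

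The cost is one extra parameter in each model and a hazard ratio that becomes conditional on entry status. No new data and no change in sample size are needed. The SAP supplied is v0.3, and its section 5.1 allows updating before sign-off. The derivation should be fixed at that stage, before outcomes are compared by arm. If the team prefers to keep the planned models as the main analysis, a prespecified sensitivity analysis with this covariate is an acceptable minimum.

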2.4.3 Exploratory endpoints/outcomes

- Mutations detected by deep sequencing compared with those detected by population sequencing
- Proportion of patients with HIV-RNA viral load < 50 copies/mL at week 4, 8, 12

* Refer to Appendices 3 (AIDS-Defining Conditions), 4 (INSIGHT Serious Non-AIDS Events Criteria), 5 (INSIGHT Progression of HIV Disease Criteria) and 6 (Immune Reconstitution Inflammatory Syndrome Generic Criteria).

3 TRIAL DESIGN

An open-label, randomised, two arm, multicentre trial over 48 weeks to compare two strategies for HIV-1 infected patients with advanced disease, stratified according to country and baseline CD4 cell count (<50 cells/ μ L, 50-199 cells/ μ L, or \geq 200 cells/ μ L).

[figure not shown]
Patients will be randomised to receive either an integrated inhibitor containing regimen (B (50mg)/F (200mg)/TAF (25mg) [1 pill administered orally once daily for 48 weeks]) or a boosted PI regimen (D (800mg)/C (150mg)/F(200mg)/TAF (10mg) [1 pill administered orally once daily for 48 weeks]).

Study visits will take place at screening, baseline, weeks 4, 8, 12, 24, 36 and 48, as well as a follow-up visit 30 days following the week 48 visit.

Routine investigations will include HIV-1 RNA, CD4, CD8, haematology (including haemoglobin, white cell count and differential, platelets), biochemistry (including sodium, potassium, creatinine, phosphorus, albumin, glucose, alanine transaminase (ALT), aspartate aminotransferase (AST), ALP, total and indirect bilirubin, total cholesterol, HDL, LDL, triglycerides), QoL questionnaire (EuroQol EQ-5D-3L), HIV Symptom Index (HIV-SI/SDM) urine sample (for haematuria, proteinuria, glycosuria, leukocytes, nitrites, pregnancy test in women of child-bearing potential (WOCBP)).

For a full list of investigations please see the table of assessments in Appendix 1.

3.1 Study Schema

4 STUDY SETTING

This study will be conducted within the NEAT ID network and include sites that have an excellent track record in clinical research and operate in up to eight countries. A full feasibility and qualification assessment plan will be undertaken for all potential sites. The sponsor will ensure that onsite visits are performed to assess GCP compliance, including (but not limited to); protocol adherence, informed consent documentation, data quality, drug accountability and overall site performance.

5 ELIGIBILITY CRITERIA

5.1 Inclusion criteria

Patients must meet all of the following inclusion criteria to be eligible for participation into this study.

1. The ability to understand and sign a written informed consent form (ICF) and must be willing to comply with all study requirements.
2. Male or non-pregnant, non-lactating females.
3. Age ≥ 18 years.
4. Has documented, untreated HIV-1 infection with either:

- a) AIDS with any CD4 cell count (AIDS-defining conditions are listed within Appendix 3).

Or

- b) Severe bacterial infection (BI)[†] and must have a CD4 cell count $< 200/\mu\text{L}$ within 30 days prior to study entry.

Or

- c) Are asymptomatic with CD4 cell count $< 100/\mu\text{L}$ within 30 days prior to study entry and must have an entry HIV viral load > 1000 copies/mL.

Or

- d) Currently receiving treatment for OI[‡].
 - i. Subjects with other serious OIs, including other AIDS-defining and AIDS-related OIs for which appropriate therapy other than ART exists are eligible, but Investigator approval must be obtained.
 - ii. Current OI treatment must have been started ≤ 14 days prior to study entry but can have been discontinued prior to study entry.

5. Have the ability to take oral medications.

6. Females of childbearing potential and heterosexually active males must be willing to use a highly effective method of contraception and be willing to continue practising these birth control methods during the trial and for at least 30 days after the last dose of study medication. See Appendix 7 for further details.

[†] A severe BI consists of any of bacterial pneumonia, IBI or any bacterial infectious disorder with grade 3 severity or requiring unscheduled hospital admission. An IBI is defined as the isolation of a bacterial organism from a normally sterile body site, or for bacterial nucleic acid to be detected at a normally sterile body site. Sterile body sites include blood, cerebrospinal fluid, pleural fluid, pericardial fluid, peritoneal fluid, joint fluid, bone aspirate, or a deep tissue abscess.

[‡] Including *Pneumocystis jirovecii* pneumonia [PCP]; disseminated histoplasmosis; cytomegalovirus [CMV] infection; toxoplasmic encephalitis; other atypical non-tuberculous, non-MAC mycobacterial infections; or other serious, invasive bacterial infections (IBI).

Such methods include:

- True abstinence from penile-vaginal intercourse, when this is in line with the preferred and usual lifestyle of the subject. (Periodic abstinence (e.g., calendar, ovulation, symptothermal, post-ovulation methods), and withdrawal are not acceptable methods of contraception).
- Non-hormonal Intrauterine device or non-hormonal intrauterine system that meets the effectiveness criteria as stated in the product label.
- Male partner sterilization prior to the female subject's entry into the study, and this male is the sole partner for that subject.
- Combined (oestrogen and progesterone containing) hormonal contraception associated with the inhibition of ovulation*:
 - Oral
 - Intravaginal
 - Transdermal
- Bilateral tubal occlusion

• Note: Non-childbearing potential is defined as either post-menopausal (had amenorrhea for at least 12 months and have an FSH (follicle stimulating hormone) of greater than 40 IU/L or, if FSH testing is not available, they have had amenorrhea for 24 consecutive months) or physically incapable of becoming pregnant with documented hysterectomy, bilateral salpingectomy or bilateral oophorectomy.

*If a patient is randomised to Syntuza, an alternative highly effective method of contraception should be used

